8.3. Time Period and Frequency for Event Assessment and Follow-Up

8.3.1. Adverse Event and Serious Adverse Event Reporting

All AEs will be collected from the time of signed ICF until the final visit.

Any AEs assessed as related to study participation (e.g., protocol-mandated procedures, invasive tests, or change in existing therapy) will be recorded from the time a subject consented to participate in the study up to and including any follow-up contact.

All SAEs will be recorded in the eCRF and reported to the Sponsor within 24 hours via email or phone (see Section 8.4).

8.3.2. Follow-Up of Adverse Events

After the initial AE/SAE report, the Investigator is required to proactively follow each subject at subsequent visits/contacts. All SAEs and nonserious AEs will be followed until resolution, until the condition stabilizes, until the event is otherwise explained, or until the subject is lost to follow-up.

The Investigator will assess the outcome of each AE using the following criteria:

- **Recovered/Resolved:** The event has improved or subject recuperated.
- Recovered/Resolved with sequelae: The subject has recuperated but retained pathological conditions resulting from the prior disease or injury.
- **Recovering/Resolving**: The event is improving.
- Not recovered/Not resolved: The event has not improved or subject recuperated.
- **Unknown**: The outcome of the event is not known, not observed, not recorded, or refused.
- **Fatal:** Termination of life as an outcome of the AE.

8.4. Reporting Procedures

8.4.1. Serious Adverse Event Reporting

When an Investigator determines that an AE meets the protocol definition of an SAE during the study, he/she must notify the Sponsor using an SAE Report Form within 24 hours of the study site personnel's knowledge of the event, regardless of the Investigator assessment of the relationship of the event to study drug. Relevant information will be entered on the AE page and on all other applicable pages of the eCRF; these pages will be submitted with the SAE Report Form.

Follow-up information received on SAEs should be emailed or faxed to the Sponsor within one business day of receipt. This information should be included on a follow-up SAE form and placed with the original SAE information.

All SAEs will be followed until resolution, until the condition stabilizes, until the event is otherwise explained, or until the subject is lost to follow-up.

The completed SAE Report form should be submitted via email or fax to the SAE Reporting Contact which can be found on the Medical Monitor/Sponsor Information Page of this protocol.

Do not delay reporting a suspected SAE in order to obtain additional information. Any additional information, if collected, can be reported as a follow-up to the initial report.

8.4.2. Regulatory Reporting Requirements for Serious Adverse Events

Prompt notification by the Investigator to the Sponsor of SAEs (even for non-interventional post-marketing studies) is essential so that legal obligations and ethical responsibilities towards the safety of subjects and the safety of a product under clinical investigation are met.

The Sponsor has a legal responsibility to notify both the local regulatory authority and other regulatory agencies about the safety of a product under clinical investigation. The Sponsor will

comply with country-specific regulatory requirements relating to safety reporting to the regulatory authority, IRB/IEC, and investigators.

Investigator safety reports are prepared for suspected unexpected serious adverse reactions according to local regulatory requirements and are forwarded to investigators as necessary.

An investigator who receives an investigator safety report describing an SAE(s) or other specific safety information (e.g., summary or listing of SAEs) from the Sponsor will file it with the investigator's brochure and will notify the IRB/IEC, if appropriate, according to local requirements.

8.5. Pregnancy Management and Reporting

Any female subject who becomes pregnant during the study will be withdrawn. Details will be collected for all pregnancies in female subjects that begin after the start of dosing and through the Follow-up visit. Pregnancy is not automatically considered an AE.

If a pregnancy is reported, then the Investigator should complete a pregnancy data collection form and submit via email or fax to the Pregnancy Reporting Contact for which contact information can be found on the Medical Monitor/Sponsor Information Page of this protocol, within 2 weeks of learning of the pregnancy. The subject will also be followed to determine the outcome of the pregnancy. Information on the status of the mother and child will be forwarded to the Sponsor. Generally, follow-up will be no longer than 6 to 8 weeks following the estimated delivery date. Any premature termination of the pregnancy will be reported.

Any SAE occurring in association with a pregnancy brought to the Investigator's attention after the subject has completed the study and considered by the Investigator as possibly related to the study drug must be promptly reported to the Sponsor or the Sponsor's representative.

The Investigator must attempt to collect pregnancy information on any female partners of male study subjects who become pregnant while the subject is enrolled in the study. Pregnancy information must be reported to the Sponsor or the Sponsor's representative as described above. The partner will also be followed to determine the outcome of the pregnancy. Information on the status of the mother and child will be forwarded to Sponsor or the Sponsor's representative. Generally, follow-up will be no longer than 6 to 8 weeks following the estimated delivery date. Any premature termination of the pregnancy will be reported on the pregnancy report form.

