1.3.1.3. Reproductive and Developmental Toxicity

Results of embryo-fetal development studies in rats and rabbits indicated an increased risk for embryo-fetal developmental effects, as evidenced by an increase in post-implantation loss and incidence of fetal skeletal variations. Results of a juvenile rat study indicated adverse microscopic changes in the form of renal pelvic dilatation in both sexes, along with reversible increases in total urinary glucose and protein excretion in males at $\geq 10/15$ mg/kg/day tapinarof (administered subcutaneously).

An investigative study in rats suggested an increased risk for hydronephrosis during a narrow window of postnatal sensitivity prior to postnatal day (PND) 32 (specifically PND 15 to 21). Rat renal tubule anatomic maturation and nephrogenesis occurs during this period [Cappon, 2010; Frazier, 2013; Zoetis, 2003], however tubule morphogenesis/nephrogenesis occurs entirely prenatally in humans [Cappon, 2010; Zoetis, 2003].

To mitigate these potential risks, women of childbearing potential (WOCBP) must utilize abstinence or a highly effective method of contraception consistently and correctly during the study and for 4 weeks after the end of treatment (Section 4.2). Pregnant women and subjects under 18 years of age will be excluded from the study. If a woman becomes pregnant during the study, she will immediately discontinue the study drug. Additionally, AEs will be monitored and clinical laboratory testing will be performed.

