3. STUDY DESIGN

3.1. Overall Design

This is a Phase 2a, multicenter, open-label study to evaluate the safety and PK of topical tapinarof cream in adults with extensive plaque psoriasis. The study will consist of three phases: Screening (up to 34 days), Treatment (29 days), and Follow-up (7-10 days).

At Day -1, eligible subjects will be enrolled into the study. During the treatment period beginning on Day 1 (Baseline), subjects will apply tapinarof cream, 1% to affected areas once a day for 29 days. Subjects will return to the clinic on Days 2, 15, 29, and 30 for study assessments and will receive a phone call on Days 8 and 22. Subjects will return to the clinic for a follow-up visit 7-10 days after the Day 29 visit. On clinic visit days, subjects will apply the study drug under the supervision of site personnel, after assessments have been completed. Full PK profiles and Holter monitoring will be collected on Day 1 and Day 29 (with corresponding 24-hour time points collected on Day 2 and Day 30, respectively). Limited PK sampling will be performed on Day 15. Pre-treatment, time-matched Holter monitoring will be conducted on Day -1 and the morning of Day 1.

Study drug will be dispensed to subjects during the clinic visits and will be administered at home between clinic visits as instructed by site personnel. Subjects will be instructed to apply study drug once daily to all affected areas, including newly appearing plaques and plaques/areas that improve during the study. Subjects will apply sufficient study drug to cover completely each lesion with a thin layer of study drug and will record the time of study drug application in a daily diary provided by the study site. Note that subjects are allowed, but not required, to treat palms, fingernails, soles, toenails, and scalp plaques with study drug. If a subject chooses to treat plaques on palms, fingernails, soles, toenails, and/or scalp, they should do so for the entirety of the treatment period from Day 1 to Day 29. Subjects will be instructed to apply study drug in the morning throughout the entirety of their participation in the study. At the phone contacts at Days 8 and 22, subjects should be reminded to complete their daily diary and bring it with them to the next clinic visit.

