3.2. Treatment Groups and Duration

All subjects will receive tapinar of cream, 1% for 29 days with once daily application.

A subject will be considered to have completed the study when he/she completes all required procedures/visits for the 29-day treatment phase.

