4.2. Inclusion Criteria

Each subject must meet all of the following criteria to be eligible to participate in the study:

- 1. Male and female subjects ages 18 to 75 years with confirmed clinical diagnosis of chronic psoriasis and stable disease for at least 6 months prior to the study;
- 2. BSA involvement ≥ 20% (the subject's scalp, palms, and soles should be excluded from the %BSA calculations to determine eligibility at Screening);
- 3. A PGA score of ≥ 3 at Screening;
- 4. WOCBP and male subjects who are engaging in sexual activity that could lead to pregnancy must use at least 1 of the following adequate birth control methods while on study and for 4 weeks after the last exposure to study drug. Acceptable contraception methods are:
 - Male or male partner with vasectomy, OR
 - Male condom AND partner use of one of the contraceptive options below:
 - Spermicide;
 - Contraceptive subdermal implant that meets effectiveness criteria including a < 1% rate of failure per year, as stated in the product label;
 - Intrauterine device or intrauterine system that meets effectiveness criteria including a < 1% rate of failure per year, as stated in the product label;
 - Oral contraceptive, either combined or progestogen alone;
 - Injectable progestogen;
 - Contraceptive vaginal ring;
 - Percutaneous contraceptive patches.

Note: Subjects using hormonal contraceptives must have been on a stable dose for at least 4 weeks before Baseline.

These allowed methods of contraception are only effective when used consistently, correctly, and in accordance with the product label. The Investigator is responsible for ensuring that subjects understand how to properly use these methods of contraception.

Non-childbearing potential is defined as premenarchal; pre-menopausal females with a documented bilateral tubal ligation, bilateral oophorectomy (removal of the ovaries) or hysterectomy; or hysteroscopic sterilization; or postmenopausal females defined as a cessation of menses for at least 12 months without an alternative medical cause. In questionable cases a blood sample with simultaneous follicle-stimulating hormone

(FSH) > 40 mIU/mL is confirmatory. Documented verbal history from the subject is acceptable.

Subjects who are abstinent are eligible, but they must agree to use one of the birth control methods listed above if they start engaging in sexual activity that could lead to pregnancy during the study.

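### Pregnancy reporting under Protocol Section 8.5 ends 18 to 21 days before the 4-week post-exposure contraception period does

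*Protocol*

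**What the plan says.** **Contraception.** Inclusion criterion 4 (Protocol Section 4.2, repeated in the Synopsis) obliges women of childbearing potential, and male subjects whose sexual activity could lead to pregnancy, to use listed "birth control methods while on study and for 4 weeks after the last exposure to study drug". Section 1.3.1.3 gives the reason: rat and rabbit studies "indicated an increased risk for embryo-fetal developmental effects". To mitigate this, women of childbearing potential must be abstinent or use a highly effective "method of contraception consistently and correctly during the study and for 4 weeks after the end of treatment".

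**Timing.** Section 3.2: "All subjects will receive tapinar of cream, 1% for 29 days with once daily application". Section 3.1: "Subjects will return to the clinic for a follow-up visit 7-10 days after the Day 29 visit".

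**Pregnancy collection.** Section 8.5 limits collection for female subjects: "Details will be collected for all pregnancies in female subjects that begin after the start of dosing and through the Follow-up visit". For male subjects it covers female partners "who become pregnant while the subject is enrolled in the study". A pregnancy in scope leads to a data collection form within 2 weeks, outcome follow-up, generally to no more than 6 to 8 weeks past the expected delivery date, and a report of any premature termination.

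**Testing.** The last scheduled pregnancy test is the urine test at Visit 8 (Table 1, Section 7.10). No later contact is scheduled.

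**The concern.** The sponsor chose 4 weeks after the last exposure as the period in which conception should be avoided. The section that says which pregnancies are documented and followed to outcome uses a shorter period and does not say why. A site that follows Section 8.5 to the letter has no instruction to report a pregnancy that began on, say, Day 45, although the subject was still bound by the contraception rule on that day.

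What is at stake is the record of any such pregnancy: the form, the follow-up to outcome, and the information on mother and child. Such a pregnancy would be rare, but it would follow maximal use of a product for which the protocol itself cites embryo-fetal findings, in a study meant to support registration.

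**Working it through.** The documents give no figure for this gap, so there is none to reproduce. The check is day arithmetic.

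**Inputs**
- Last application for a completer: Day 29 (Sections 3.2 and 7.8; Section 7.9 lists none on Day 30).
- Post-exposure contraception: 4 weeks = 28 days (Sections 1.3.1.3 and 4.2).
- Follow-up visit: 7 to 10 days after Day 29 (Sections 3.1 and 7.10).
- End of collection for female subjects: pregnancies that begin by Follow-up (Section 8.5).

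**Calculation for completers**
- Contraception ends: 29 + 28 = Day 57.
- Follow-up: 29 + 7 = Day 36, to 29 + 10 = Day 39.
- Gap = end of contraception minus Follow-up day.

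| Follow-up | Gap (days) | Gap (weeks) | Share of the 28 days |
|---|---|---|---|
| Day 36 | 57 − 36 = 21 | 3.0 | 21/28 = 75% |
| Day 39 | 57 − 39 = 18 | 2.6 | 18/28 = 64% |

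**Early terminators.** No interval is set between the last dose and the Early Termination visit. On the assumption that this visit closes collection and falls on the day of the last dose, the gap would be up to about 28 days.

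**Partners.** The 4-week rule reaches male subjects through Section 4.2; Section 1.3.1.3 speaks only of women. Section 8.5 does not define when enrolment ends. If it is taken to end at Follow-up (an assumption), the gap is the same 18 to 21 days.

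**Other routes that might cover those days**
- Section 8.5 requires prompt reporting, after study completion, of a serious adverse event associated with a pregnancy if it reaches the investigator and is considered possibly related.
- Section 8.1 asks for prompt notice of any serious adverse event learned of after discharge and considered reasonably related, but does not oblige investigators to look for events in former subjects.
- Section 8.1.3 counts a congenital anomaly or birth defect as serious.
- Section 8.5 says that pregnancy is not automatically an adverse event, so adverse event reporting does not by itself capture an uncomplicated pregnancy.

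These routes can bring in some bad outcomes. None brings in the pregnancy itself.

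**Expected number (illustration).** Suppose that all 20 subjects were at risk for the full 21 days: 20 × 21/365.25 = 1.15 person-years. With assumed annual pregnancy rates of 1% to 10%, this gives 1.15 × 0.01 = 0.01 to 1.15 × 0.10 = 0.12 pregnancies. The rates are not from the documents. The true figure should be lower, because many subjects aged 18 to 75 will not be at risk.

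**The case against.** The strongest reply is that nothing here is contradictory. Section 4.2 tells subjects what precaution to take; Section 8.5 tells sites what data to collect. Both can be obeyed at once, and no passage says that the two periods must be equal. That stands: this is an unexplained difference between two periods, and a reader who inferred a contradiction would go too far.

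A reader might also infer three stronger points that the documents do not support.
- **That the last weeks are wholly unobserved.** The post-study duties in Sections 8.1 and 8.5 remain, and birth defects count as serious under Section 8.1.3. They are passive and limited to possibly related serious events, but they exist. A pregnancy that began before Follow-up also stays in scope if it is found later, although no later test or contact is planned to find it.
- **That every conception in those weeks is a drug-exposed pregnancy.** Section 1.3.1.3 presents the 4 weeks as a precaution. Section 1.2 says that plasma levels peak in the first week and fall to or near the limit of detection with continued dosing, without accumulation. That could justify a narrower collection period, but the protocol does not use it for that purpose and keeps the 4 weeks.
- **That the study loses data it was designed to produce.** Pregnancy outcome is not among the objectives or endpoints in Section 2, and SAP Section 10.8 only lists pregnancy test results.

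It can also be argued that Section 8.5, where it says what to do once a pregnancy is reported, has no end date. Read after the sentence that sets the period, it prescribes the form and the deadline and does not clearly widen the scope. At best, sites are left unsure.

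**Conclusion.** The point holds as a gap in safety reporting. For completers, 18 to 21 of the 28 post-exposure days (64% to 75%) lie outside the collection rule for female subjects. The same applies to partners if enrolment ends at Follow-up. Pregnancies that begin in those days are outside pregnancy reporting and outcome follow-up, apart from possibly drug-related serious events that come to the investigator's notice.

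The practical weight is small: well under one expected pregnancy under the illustrative rates, and no effect on any planned analysis. The result assumes a last application on Day 29 and a Follow-up visit within its stated range. The documents do not show which of the two periods is the right one, and this review takes no position on that. It is a cheap improvement of low priority.

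**What to change.** Reconcile the pregnancy-collection period in Section 8.5, for female subjects and for partners of male subjects, with the post-exposure contraception period in Sections 1.3.1.3 and 4.2. The sponsor should set the duration. In the same edit, state when enrolment ends for the partner rule, and how the period runs for subjects who stop early.

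If the periods are aligned, sites would report any pregnancy they learn of that began within the period, and would remind subjects of this at the Follow-up visit. If the sponsor prefers to keep them different, a sentence giving the reason would settle the matter.

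The cost is protocol wording and a reminder at a visit that already takes place. No visit, test or analysis is added. The downside is a little passive reporting after the last visit.

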8.6. Safety Oversight

No independent Data Monitoring Committee will be used for this study; however, the Sponsor (including the Medical Monitor) will monitor safety on a periodic basis throughout the study.

9. DATA MANAGEMENT

For this study, subject data will be entered into the Sponsor defined eCRFs, transmitted electronically to the Sponsor or designee and combined with data provided from other sources in a validated data system.

Management of clinical data will be performed in accordance with applicable Sponsor standards and data cleaning procedures will be used to ensure the integrity of the data, e.g., errors will be corrected, and inconsistencies queried in the data.

AEs and relevant medical history will be coded using the most current version of the Medical Dictionary for Regulatory Activities. Concomitant medications will be coded with the most current version of World Health Organization Drug Global Dictionary.

The Investigator will retain original source documents and the Sponsor will receive eCRF-required data as electronic datasets. Subject initials will not be collected or transmitted to the Sponsor.

10. STATISTICAL CONSIDERATIONS AND DATA ANALYSES

This study will evaluate the safety and PK of tapinar of cream, 1% in adults with plaque psoriasis.

10.1. General Considerations

All study data will be summarized using descriptive statistics. Categorical variables will be reported using frequency and percentage (e.g., gender, race). Continuous variables will be reported using number of subjects, mean, standard deviation (SD), median, minimum, and maximum. All safety and PK data will be listed by subject.

10.2. Determination of Sample Size

This study will be conducted to evaluate the safety and PK of tapinarof cream, 1% in adult subjects with extensive plaque psoriasis. There is no formal statistical hypothesis planned and the sample size is mainly based on feasibility and an estimated number of subjects needed to address the objectives of the study.

10.3. Analysis Sets

10.3.1. Safety Analysis Set

All randomized subjects who receive at least 1 application of study drug will be included in the safety analysis set. Subjects will be analyzed as treated.

10.3.2. PK Analysis Set

All subjects who have at least 1 application of study drug and have at least 1 evaluable PK assay result will be included in the PK analysis set. A value that is below the limit of quantification is considered evaluable.

10.3.3. QT/QTc Analysis Set

The QT/QTc analysis set will include all subjects in the safety analysis set with measurements at Baseline as well as on-treatment with at least 1 post-dose time point with a valid Δ QTcF value.

10.3.4. PK/QTc Analysis Set

The PK/QTc analysis set will include all subjects who are in both the QT/QTc and PK analysis sets with at least 1 pair of post-dose PK and QTcF data from the same time point.

10.4. Planned Analyses

All safety and PK measures over the course of the study will be presented. Details of planned analyses will be described in the statistical analysis plan (SAP) which will be finalized prior to database lock.

10.4.1. Disposition and Demographics

Demographic and Baseline characteristics as well as medical history will be summarized using the safety analysis set, including frequency and percentages for categorical variables and mean, SD, median, minimum, and maximum for continuous variables.

